The study will consist of three (to a maximum of six) sequential cohorts of approximately 10 participants each. The cohorts will be dosed one after the other for a total of 30 (to a maximum of approximately 60) participants. This is an adaptive study and for a particular cohort, safety, incidence of infection and incidence of clinical illness will be evaluated on Day 14 to inform whether the ABO809 dose needs to be changed for dosing of the next cohort (see Section 6.5.1). If there are no safety issues, and the expected incidence of infection and illness are observed in one cohort, the next cohort will be dosed at the same dose level (see Section 6.5.1 for details). If the dose of ABO809 is changed from one cohort to the next, additional cohorts may be added to further evaluate Cryptosporidium infection and clinical illness following dosing with ABO809.

The study will consist of up to a 28-day Screening/Baseline period, an ABO809 administration and inpatient monitoring period, an outpatient follow-up period, and a study completion evaluation on Day 56. Additionally, Post-Study Follow-Up Calls will be conducted at 6 and 12 months after ABO809 administration. A CHIM diary will be provided to each participant to collect information on the participant's clinical symptoms.

Participants will receive a single oral dose of ABO809 on Day 1.

Cryptosporidium infection is defined as the presence of oocysts in at least 1 stool sample starting 72 hours following the administration of ABO809 (or sooner if associated with symptoms suggestive of diarrheal illness) and up to Day 10.

If clinical symptoms associated with cryptosporidiosis occur earlier than 72 hours post-administration, then stool samples after the onset of symptoms can be collected for parasitological evaluation for the primary endpoint. Normal bowel transit time varies from 30 to 40 hours, and therefore \geq 72 hours is chosen to minimize the chance of detecting only passively excreted oocysts given orally.

Resolution of *Cryptosporidium* infection is defined as no evidence of *Cryptosporidium* in stool samples collected over ≥ 2 consecutive days.

Stool samples will also be collected and sent to the laboratory in instances of relapse symptoms suggestive of *Cryptosporidium* infection until Day 28. Participants experiencing diarrheal symptoms between Day 28 and Day 56 may return for an unscheduled visit and provide stool for assessment of *Cryptosporidium* infection.

[figure not shown]

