A participant will be considered as showing clinical diarrheal illness if diarrhea is observed with at least two diarrheal bowel events within 24 hours on at least two days during the observation period beginning after the ABO809 administration (Day 1) and ending on Day 28 (see Section 8.3.2)

Resolution of diarrheal illness from Cryptosporidium infection requires ≥ 2 consecutive days with no diarrheal stools (stool sample grades 1 or 2).

Participants will be monitored daily for infection (parasitological evaluation) and diarrheal illness (clinical evaluation) during the domicile period. The monitoring of symptoms will continue in the outpatient setting with the collection of information via the CHIM diary and Safety Follow-Up Calls. Participants will provide a health and stool update daily from Day 1 through 28 in the CHIM diary. Safety Follow-Up Calls will occur on Days 35, 42, 49, and 56.

The primary endpoint is *Cryptosporidium* infection as indicated by detection of oocysts in fecal samples by EIA CCI ≥72 hours following an oral administration of ABO809 (or sooner if associated with symptoms suggestive of diarrheal illness). Secondary endpoints include characterization of diarrheal illness, safety and tolerability.

Figure 3-1 Study Design

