3.3 Follow-up period and End of Study

Participants will return for outpatient follow-up visits on Day 14, 17, 21, 24, and 28 for clinical assessments and to provide collected stool samples for analysis. To minimize the risk of long term asymptomatic shedding and recurrence, participants may receive nitazoxanide per the U.S. Prescribing Information (see Section 6.2.3).

If a participant experiences diarrhea after Day 10 (after the participant has been discharged from the study site), the participant may be readmitted, at the discretion of the Investigator, to remain domiciled until the cessation of symptoms or Day 21, whichever is earlier. If diarrhea is not associated with any additional risks to participants, the Investigator can decide that the participant can be managed in an outpatient setting. In this case, the participant is requested to make a reasonable effort to collect all diarrheal stool samples for delivery to the study site. If a participant is still experiencing diarrheal illness at Day 28, the participant's stool will be analyzed for ongoing shedding of oocysts and the participant may be referred to specialty care for further diagnostic work-up and treatment at the discretion of the Investigator.

All participants will return for a follow-up visit on Day 28 to provide collected stool samples. A physical examination and laboratory tests will also be conducted.

Commercially Confidential Information

Alternatively, between

Day 28 and Day 56, participants may seek medical support from his/her healthcare provider (HCP). Participants may come back to the study site for an unscheduled visit until EOS. The end of study (EOS) visit will occur on Day 56 via phone call. Additional Post-Study Follow-Up phone calls will be conducted after EOS at 6 and 12 months after ABO809 administration. During the phone calls, data will be collected on the development of new onset persistent symptoms that may be related to administration with ABO809, including but not limited to diarrhea, abdominal pain, eye pain and joint pain in all participants (see Section 10.1.1.1).

4 Rationale

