Outpatient follow-up period: After the domicile period, participants will be followed on an outpatient basis ending on Day 56 following the ABO809 administration. Infection is expected to be self-limiting in healthy adults and resolve by Day 21. Published literature on the intensity of infection and oocyst excretion patterns of *C. parvum* in healthy volunteers suggests that oocyst excretion is limited to the first 14 days in up to 86% participants with diarrhea, and excretion prolonged beyond 28 days is observed in only 5% of participants (Chappell et al 1996). Participants will return for follow-up visits on Day 14, 17, 21, 24 and 28 for physical examination and/or to provide collected stool samples (for measurement of oocyst shedding) (see Table 8-1). Safety Follow-Up Calls will be conducted with participants up to Day 56 to collect adverse events that are considered related to administration with ABO809 (see Section 10.1.1.1). Any participants who experience diarrheal symptoms between Day 28 and Day 56 may provide a stool sample for analysis and may return to the study site for an unscheduled visit to consult with the Investigator.

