6.2.4.2 Other restrictions

- No strenuous physical exercise (e.g. weight training, aerobics, football) from Day 1 until discharged
- Participants must abstain from using public pools and waterparks from Day 1 until after the Day 28 visit. Refraining from using private swimming pools is also recommended.

- Employment as a healthcare worker with direct patient care, in a daycare center (for children or the elderly), or direct food handler (individuals who work directly with food in commercial establishments) is prohibited between Screening and Day 28.
- Sharing a home with a pregnant woman or anyone <7 years old or >65 years old, infirmed, or immunocompromised is prohibited between Screening and Day 28.
- Sexual practices that may increase the risk of fecal-oral transmission of *Cryptosporidium* should be avoided or appropriate safety measures used from Day 1 until after the Day 28 visit. Participants will be informed about CDC recommendations to practice safer sex in case of cryptosporidiosis.

(Parasites-Cryptosporidium-Prevention & Control-General Public 2019):

- Wait to have sex (vaginal, anal, and oral) for 2 weeks after you no longer have diarrhea
- Reduce your contact with stool during sex by:
 - Washing your hands, genitals, and anus with soap and water before and after sexual activity
 - Using barrier methods during sex. Barrier methods include condoms, dental dams, and cut-open condoms. Sex includes oral (mouth-to-penis, mouth-to-vagina, mouth-to-anus), anal (penis-to-anus), and vaginal (penis-to-vagina) sex
 - Using latex gloves during anal fingering or fisting
 - Using condoms the right way, every time you have anal and vaginal sex, which will also help prevent other sexually transmitted infections
 - Washing your hands with soap and water immediately after touching a used condom or other barrier method
 - Washing sex toys with soap and water after each use, and washing hands after touching used sex toys

Participants will receive educational material explaining all applicable restrictions and recommendations to avoid spread of *Cryptosporidium* oocysts.

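### Protocol 6.2.4.2 ends the household, work and public-pool restrictions at a fixed Day 28, with no visible condition for a participant still positive or ill then

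*Protocol*

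**What the plan says.** Three protections in Protocol 6.2.4.2 end on a date. Living with a pregnant woman or with "anyone <7 years old or >65 years old, infirmed, or immunocompromised is prohibited between Screening and Day 28". The ban on direct patient care, daycare work and commercial food handling has the same end-date. For pools: "Participants must abstain from using public pools and waterparks from Day 1 until after the Day 28 visit". The precautions on sexual practices also run until after the Day 28 visit, but the public-health advice listed under them has no calendar cap: "Wait to have sex (vaginal, anal, and oral) for 2 weeks after you no longer have diarrhea".

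The protocol also anticipates participants who are not clear by Day 28:

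- Section 3.3: "If a participant is still experiencing diarrheal illness at Day 28", the stool is tested for oocysts and the participant may be referred to specialty care.
- Section 4.1 cites published challenge data in which "excretion prolonged beyond 28 days is observed in only 5% of participants".
- Section 10.1.1.1 makes oocysts found in stool after nitazoxanide an adverse event of special interest.
- Section 3: "Participants experiencing diarrheal symptoms between Day 28 and Day 56 may return for an unscheduled visit and provide stool for assessment". Section 3.3 adds: "Participants may come back to the study site for an unscheduled visit until EOS".

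None of this visible text changes the end-dates in 6.2.4.2.

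**The concern.** The risk falls on people who are not in the trial. Section 1.1 describes infection as protracted and potentially life threatening in children aged 0-2, malnourished children and immunocompromised people. Section 4.1 gives protection of household contacts and public health as a reason for treating participants. Yet under the visible text, someone known to be positive or ill at Day 28 could move into a home with an infant, start food handling or use a public pool after that date without breaching the protocol.

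A calendar rule is also out of step with the rest of the plan. Release from the unit after Day 10 requires at least 24 hours without diarrheal stools (3.2), and Section 3 already defines resolution of both infection and diarrheal illness. The Day 28 stool is tested in any case, so the information for a conditional release is largely collected already.

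**Working it through.** The plan gives no count of late shedders to reproduce, so the check has a textual part and a numerical part.

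**Text.** Each end-date was compared with any condition attached to it.

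- Household: ends Day 28; no visible condition.
- Work: ends Day 28; no visible condition.
- Public pools: end after the Day 28 visit; no visible condition.
- Sexual practices: precautions end after the Day 28 visit. The 2-week wait after diarrhea covers people who have been ill, but not positive participants without diarrhea.

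The SAP has no such condition either.

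**Inputs for the size.**

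- Dosed: 30, up to about 60 (Section 3).
- Infected: 90-100% (1.2).
- Shedding beyond 28 days: 5% (4.1). The sentence can be read as 5% of all infected or 5% of those with diarrhea, so both are used. It is taken to describe shedding without nitazoxanide, which the protocol does not state.
- Diarrheal illness: 60-70%, the target in 6.5.1.
- Nitazoxanide efficacy: 80-93% (4.1), leaving a residual of 7-20%. Applying this to late shedders is an assumption, because 4.1 says the effect on long-term shedding has not been studied.

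**Expected late shedders with no treatment effect** = dosed × share at risk × 0.05.

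- 5% of all infected: 30 × 0.90 × 0.05 = 1.35, to 60 × 1.00 × 0.05 = 3.0.
- 5% of those with diarrhea: 30 × 0.60 × 0.05 = 0.9, to 60 × 0.70 × 0.05 = 2.1.
- Combined range: 0.9 to 3.0.

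**Expected late shedders with treatment** = the above × residual.

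- Low: 0.9 × 0.07 = 0.063.
- High: 3.0 × 0.20 = 0.60.

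**Chance of at least one, treated**, with participants independent = 1 − (1 − share at risk × 0.05 × residual)^dosed.

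- Low: 1 − (1 − 0.60 × 0.05 × 0.07)^30 = 0.06.
- High: 1 − (1 − 1.00 × 0.05 × 0.20)^60 = 0.45. This needs 60 dosed, all infected and the lowest efficacy together.
- Middle (90% infected, efficacy 86.5%, residual 13.5%): with 30 dosed, 0.18 expected and a chance of 0.17; with 60 dosed, 0.36 expected and a chance of 0.31.

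The chance of none is therefore 55% to 94%.

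**Extra stool samples** for one clearance attempt = 2 days × 1-3 stools = 2-6. The limit of three tested stools a day in 8.3.1 is stated for domiciled days and is assumed here. Across the trial this is 0.063 × 2 = 0.13 to 0.60 × 6 = 3.6 expected with treatment, and 0.9 × 2 = 1.8 to 3.0 × 6 = 18 with no treatment effect. Repeat attempts, and participants who are ill but not shedding, are not counted.

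**The case against.** The strongest objection is redaction. A blacked-out block in 3.3 comes directly before the text on Day 28 to Day 56, most of 5.2 is hidden, and the participants' education material is not supplied. A reader might infer that the plan has no rule at all for late shedders; the documents cannot show that. What stands is narrower: the end-dates in 6.2.4.2 are unredacted and carry no condition.

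Second, much is already done. Every infected participant is due nitazoxanide on Day 21 or once the Day 17 result is available, and from Day 10 if diarrhea persists. A second course or other drugs may follow (6.2.3), adverse events are followed up, the hygiene and cleaning advice has no end-date, and household contacts are tracked to Day 56 (SAP 1.1). Section 4.1 says all earlier challenge participants cleared infection, though not by when. These measures make late shedding less likely, treat it or record it. They do not extend the restrictions.

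Third, a reader might take 0.9-3.0 as the forecast for this trial. It is not, because it ignores the planned treatment. Nor do any of these figures count exposed contacts: the share of late shedders who would enter a restricted home, job or pool after Day 28 is not in the documents and could be anything from 0 to 100%. The household and work bans start at Screening, so exposure needs a return or a new entry while still shedding. Both objections stand and limit the size of the point.

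Finally, two negative days is an endpoint definition, and SAP 2.4.1 acknowledges that shedding varies from stool to stool and day to day. It should therefore be a minimum for release, not proof of clearance.

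**Conclusion.** The point holds as a gap in the visible release rule. Followed as written, 6.2.4.2 would release a participant known to be positive or ill at Day 28 from the household, work and pool restrictions. The expected number is below one with treatment (0.06-0.6), and none is the likeliest outcome. That rests on 80-93% efficacy applying to late shedders, on the cited 5% carrying over to this trial, and on independence between participants. The case for changing the text rests on the possible severity of harm to third parties and the low cost, not on frequency.

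Two further inferences should be avoided. It would be wrong to say that all sexual-contact precautions lapse at Day 28, since the 2-week advice continues for anyone who has had diarrhea. And the window of 4 to 7 days after treatment in 6.2.3 does not justify Day 28 as the trigger: it describes clinical response, not oocyst clearance. Day 28 is suitable because it is the last scheduled stool test. The primary endpoint and its analysis are unaffected.

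**What to change.** Keep Day 28 as the minimum and add to 6.2.4.2:

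1. For participants who have had an infection or have ongoing diarrheal illness, hold the household, work and pool restrictions and the sexual-practice precautions until the Day 28 EIA result, confirmed by DFA if positive, is known.
2. If that result is positive, or diarrheal illness is ongoing at Day 28, continue them at least until the Section 3 criteria are met: no *Cryptosporidium* in stools over at least 2 consecutive days, and at least 2 consecutive days without diarrheal stools. The trigger should be ongoing diarrheal illness, not a single loose stool.
3. Confirm this at the unscheduled visits already allowed until end of study, and open them explicitly to positive participants without symptoms.
4. State that the 2-week sexual-contact advice still applies where it is longer.
5. Give the last scheduled stool test as the reason for the Day 28 trigger.

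If a redacted section already holds such a rule, a cross-reference from 6.2.4.2 is enough.

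The cost is a few sentences there and in the education material. Some sampling is new, because stool testing after Day 28 is described only for participants with diarrheal symptoms: about 2-6 samples per affected participant for each clearance attempt. Previously infected or still-ill participants wait for the Day 28 result. Turnaround is not stated; up to about 4 days is assumed from the Day 17 to Day 21 interval in 6.2.3. A very few participants stay restricted longer.

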6.2.4.2.1 Additional Recommendations

Handwashing Procedures

Alcohol-based sanitizers are not effective against *Cryptosporidium*. Use of good hygiene practices, especially washing hands with soap and water is essential, in particular at the following key times (When and How to Wash Your Hands 2020):

- Before, during, and after preparing food
- Before and after eating food
- Before and after caring for someone who is sick with vomiting or diarrhea
- Before and after treating a cut or wound
- After using the toilet
- After changing diapers or cleaning up a child who has used the toilet
- After blowing your nose, coughing, or sneezing

- After touching an animal, animal feed, or animal waste
- After handling pet food or pet treats
- After touching garbage
- There can also be other times when it is important to wash hands

House-cleaning Procedures

Participants will be informed that *Cryptosporidium* is not sensitive to chlorine or bleach disinfectants and no disinfectant is completely effective against *Cryptosporidium*. The chance of spreading the infection can be lowered by recommended cleaning procedures, which will be provided to the participants:

(Parasites – Cryptosporidium – General Information for the Public)

- Wash linens, clothing, dishwasher- or dryer-safe soft toys, etc. soiled with feces or vomit as soon as possible
- Flush excess vomit or feces on clothes or objects down the toilet
- Wash linens, clothing, etc. soiled with feces or vomit as soon as possible
- Use laundry detergent and wash in hot water (113°F or hotter for at least 20 minutes or 122°F or hotter for at least 5 minutes)
- Machine dry on the highest heat setting

For other household objects and surfaces:

- Remove all visible feces
- Clean with soap and water
- Let dry completely for at least 4 hours (if possible, expose to direct sunlight during the 4 hours)

6.3 Participant numbering, treatment assignment, randomization

6.3.1 Participant numbering

Each individual may participate only once in this study and will be identified by a Participant Number (Participant No.) that will be assigned when the participant is enrolled for screening and will be retained for the participant throughout his/her participation in the study. A new Participant No. will be assigned at every subsequent enrollment if the participant fails screening and is re-screened. The Participant No. consists of the Center Number (Center No.) (as assigned by Novartis to the investigative site) with a sequential participant number suffixed to it, so that each participant's participation is numbered uniquely across the entire database. Upon signing the informed consent form, the participant is assigned to the next sequential Participant No. available.

The informed consent procedures need to be re-started if the Investigator chooses to re-screen the participant after a participant has screen failed, and the participant will be assigned a new Participant No.

6.4 Treatment blinding

Treatment will be open to participants, investigator staff, person performing the assessments and the Novartis clinical trial team (CTT).

6.5 Dose escalation and dose modification

Prior to any dose adjustment, a review of efficacy and safety/tolerability data in the dose cohort will be performed, in order to decide about dose escalation.

6.5.1 Dose escalation guidelines

Data to be reviewed for dose escalation

After each cohort, and prior to any dose adjustment for the subsequent cohort, a review of all available safety data will be performed to determine if it is safe to dose additional participants in subsequent cohorts.

The data to be reviewed to inform dose-adjustment include the incidence of clinical symptoms and the incidence of infection up to Day 10, as well as all available safety information including safety information obtained up to Day 14, AEs, safety laboratory assessments (hematology, chemistry, urinalysis), ECGs, vital signs, physical examination) for that cohort.

Criteria for dose escalation

The Sponsor and site Investigator will perform a joint Dose Adjustment Data Review after all participants in a cohort have completed the Day 14 visit, with the expectation that 10 participants will provide evaluable data. Evaluable data is defined as data received from any participant who provided at least one stool sample for parasitological assessment and/or in whom we have a clinical evaluation of potential diarrheal illness via CHIM diary or AE reporting with at least two diarrheal bowel events within 24 hours after ≥72 hours post administration of ABO809. For definitions of infection and diarrheal illness, see Section 3. If there are no safety concerns that will prevent continuation of a given dose level or dose escalation, the dose escalation decision will be guided by the following criteria. If at the data review the criteria below are achieved, a subsequent cohort may be dosed at the current dose level:

- There are approximately 80%-90% of participants showing infection
- There are approximately 60%-70% of participants showing diarrheal illness

Otherwise, a dose escalation decision may be made. The decision will take into consideration the totality of data available at the time of decision making.

In the case of safety concerns associated with any ABO809 dose, the next cohort may be dosed with an inoculum approximately one order of magnitude smaller than the preceding one. For example, if safety concerns are noted in the cohort receiving an inoculum of approximately 10⁶

oocysts, the next cohort of 10 participants may be dosed with an inoculum of approximately 10⁵ oocysts (see Section 6.5.1.2).

Safety Review Team

Participating functions (tasks can be delegated to appropriately qualified deputies) in all safety reviews include:

- Sponsor
 - medical lead
 - operational lead
 - research lead (optional)
 - statistician (optional)
 - biomarker expert (optional)
- Study site
 - Investigator
 - operational lead

Additional functions can be added on an ad-hoc basis.

For timing of safety data reviews see Section 4.4 (Purpose and timing interim analyses), Section 6.5.1 (Dose escalation), and Section 9.1.4 (Study stopping rules).

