1.2 Purpose

The goal of this Phase I CHIM study will be to determine if oral administration of a Good Manufacturing Practice (GMP) supply of *C. parvum* oocysts (ABO809) to healthy volunteers results in *Cryptosporidium* infection and diarrheal illness. The study will measure fecal *Cryptosporidium* oocysts (parasitological endpoint) as well as diarrhea and associated signs and symptoms (clinical endpoint).

It is expected that approximately 90-100 percent of participants receiving ABO809 may become infected. The incidence of diarrheal illness will also be evaluated and may be somewhat lower than the incidence of infection.

This study, if successful, would enable a robust CHIM model that can be used in future studies to evaluate the efficacy of novel therapies and vaccines for the treatment and prevention of *Cryptosporidium* infection in healthy participants before they are assessed in the pediatric target population.

Amended Protocol Version v02 (Clean)

2 Objectives and endpoints

Objective(s)	Endpoint(s)		
Primary objective(s)	Endpoint(s) for primary objective(s)		
 To evaluate the incidence of Cryptosporidium infection following an oral administration of ABO809 	Cryptosporidium infection as indicated by Cryptosporidium oocysts in fecal samples measured by EIA CCI at ≥72 hours post-administration (or sooner if associated with symptoms of diarrheal illness) up to Day 10 (inclusive).		
Secondary objective(s)	Endpoint(s) for secondary objective(s)		
To evaluate the incidence and characteristics of diarrheal illness	 Presence of clinical diarrheal illness by Day 10 (inclusive) and Day 28 		
following an oral administration of ABO809	 Number of diarrhea episodes 		
	Stool weight		
	Grading of stool consistency		
	 Time to onset and time to resolution of diarrheal illness 		
	 Characteristics of clinical signs and symptoms associated with clinical diarrheal illness such as (abdominal pain, abdominal cramping, nausea, vomiting, fever, electrolyte imbalance, dehydration) up to Day 28 		
	Cryptosporidium infection as indicated by Cryptosporidium oocysts in fecal samples measured by EIA CCI at ≥72 hours post-administration (or sooner if associated with symptoms of diarrheal illness up to Day 28)		

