 To evaluate the time to onset and resolution of Cryptosporidium infection in participants who developed an infection following an oral administration of ABO809 	 Detection of fecal shedding of C. parvum oocysts by EIA CCI up to 28 days after administration of ABO809 		
	 Time to onset and time to resolution of Cryptosporidium infection following an oral administration of ABO809 		
 To assess the safety and tolerability of ABO809 	 Adverse events, vital signs, ECG findings, safety laboratory assessments including chemistry, hematology, and urinalysis results up to and including the Day 28 visit 		
	 Adverse events of special interest by telephone follow-up after Day 28 through 12 months after ABO809 administration 		

Objective(s) Endpoint(s)

Commercially Confidential Information

3 Study design

This Phase 1 Cryptosporidium CHIM study employs a single-center, open-label design to characterize the incidence of infection and associated symptoms following the administration of single doses of *C. parvum* oocysts (ABO809).

The study will enroll healthy volunteers in cohorts of approximately 10 participants who will receive ABO809 on the same day. A dose level group will receive the same ABO809 dose and can be comprised of multiple cohorts. The first dose level group will start with a cohort of 10 participants who will receive ABO809 at a dose of 1x10⁴ oocysts. The study will continue to enroll participants in the same dose level group if the desired incidences of infection and diarrheal illness are observed, up to a total of approximately 30 participants. If the desired incidences of infection and diarrheal illness are not observed, a new dose level group, receiving ABO809 at a dose of 1x106 oocysts, may be initiated. If needed to optimize the model, intermediate ABO809 doses may be evaluated (see Section 6.5).

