Treatment with nitazoxanide: Nitazoxanide is a safe and well-tolerated drug approved in the United States to treat diarrhea caused by Cryptosporidium parvum. In a 2015 C. muris challenge study, two subjects with persistent oocyst shedding were successfully treated with nitazoxanide and the infection was resolved in both subjects, demonstrating the potential of nitazoxanide as a rescue drug (Chappell et al 2015). Following resolution of diarrhea, C. parvum infection may be associated with shedding of oocysts with a 21% relapse rate as suggested by the 1993 Milwaukee outbreak (MacKenzie et al 1995). Participants who develop an infection (i.e. oocyst shedding), with or without clinical symptoms will receive a standard 3-day course of nitazoxanide treatment per the U.S. Prescribing Information on Day 21. Given the variability in the onset and duration of oocyst shedding and clinical symptoms in healthy adults. administering nitazoxanide on Day 21 is considered appropriate to enable the full characterization of the study endpoints. Nitazoxanide may be administered earlier, based on clinical findings (see Section 3.3 and Section 6.2.3). Once initiated, nitazoxanide treatment is expected to decrease or eliminate any persistent oocyst shedding to safeguard participants, their household contacts and public health interests. Participants will be informed about reasons of nitazoxanide treatment to improve compliance, which will be recorded in a participant diary. Although nitazoxanide has proven efficacy in reducing oocyst shedding and acute diarrhea in 80-93% of treated participants, there have been no studies looking at the effect of nitazoxanide on the incidence of long-term oocyst shedding or sequelae of cryptosporidiosis. Given this background, Safety Follow-Up Calls will be conducted up to Day 56.

Adaptive study design: The goal is to maximize the incidence of infection. The study cohorts of approximately 10 participants each are designed to enable domiciling of participants in an inpatient unit with adequate infection control, isolation and monitoring. Cohorts are sequential to enable adjustment of the ABO809 dose from one cohort to the next for efficacy and safety reasons. After the Day 14 visit, a Dose Adjustment Data Review will be conducted for the

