cohort (see Section 6.5.1) and may result in a dose adjustment for the subsequent cohort. The dose may be adjusted upward to increase the incidence of infection and clinical symptoms or may be reduced due to safety concerns.

End of the Study (EOS): For each participant, the study will end at the Day 56 visit. Additional Post-Study Follow-Up phone calls will be conducted after EOS at 6 and 12 months after ABO809 administration.

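### The repeat-dose criteria in Protocol 6.5.1 are written as ranges with upper ends, so a cohort that does better than the range falls under the escalation branch; they should be stated as minimums

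*Protocol*

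**What the plan says.** Protocol 6.5.1 (Dose escalation guidelines) sets out a joint sponsor and investigator review after a cohort's Day 14 visit, with 10 evaluable participants expected. If safety allows, a further cohort may receive the same dose when two criteria are achieved:

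- "There are approximately 80%-90% of participants showing infection"
- "There are approximately 60%-70% of participants showing diarrheal illness"

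The next sentence covers every other result: "Otherwise, a dose escalation decision may be made". The section adds that the totality of the data will be considered. Its only other branch is a dose reduction for safety concerns. Nothing addresses results above the two ranges.

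Other sections describe the same decision differently:

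- Section 1.2: "It is expected that approximately 90-100 percent of participants receiving ABO809 may become infected".
- Section 3, on escalation: "If the desired incidences of infection and diarrheal illness are not observed, a new dose level group" may be started at 10^6 oocysts.
- Section 3, on repeating, provided there are no safety issues: if "the expected incidence of infection and illness are observed in one cohort, the next cohort will be dosed at the same dose level". The reader is sent to 6.5.1 for details.
- Section 4.1: "The goal is to maximize the incidence of infection", and "The dose may be adjusted upward to increase the incidence of infection and clinical symptoms", with reduction only for safety.
- Section 4.2: the study seeks to maximize infection and symptoms safely. It escalates when the desired incidence of either is not achieved, again with a reference to 6.5.1.

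**The concern.** Outside 6.5.1 the target incidences work as minimums: a shortfall leads to a higher dose and success leads to a repeat. Inside 6.5.1 they are ranges with a top. As written, 10/10 infected is above the infection range and 8/10 ill is above the illness range, so either result sends the cohort to the escalation branch. The infection range ends at 90%, which is where the expected range in Section 1.2 begins. No visible passage gives a reason to cap either rate.

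The anticipated next dose level after 10^4 oocysts is 10^6, a 100-fold step in healthy volunteers. Section 4.2 notes that in the earlier study supporting 10^6, only seven people received 1,000 oocysts or more. The text governing that step should not open it after a fully successful cohort.

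**Working it through.** **Figures the protocol already gives.** Sections 12.8.1 and 12.8.2 state the lower limits that can be claimed with at least 80% chance. Method: take the largest count x with P(X ≥ x) ≥ 0.80, then the one-sided 80% exact lower limit at x.

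| True rate | n = 20 | n = 30 | n = 60 |
|---|---|---|---|
| 90%, computed | 74.1% | 78.6% | 81.6% |
| 90%, stated | 74% | 78% | 81% |
| 70%, computed | 48.1% | 53.99% | 58.8% |
| 70%, stated | 48% | 53% | 58% |

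All six agree once truncated to whole percent. They are not in dispute; they supply the planning rates used below.

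**Inputs for the cohort rule.** n = 10 (6.5.1); infection rate 0.90 (12.8.1); illness rate 0.70 (12.8.2, given there for clinical symptoms). Assumption: illness occurs only in infected participants. Then infected I ~ Bin(10, 0.9), and ill given I ~ Bin(I, 0.7/0.9).

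**Two readings.** Literal: 8-9 infected and 6-7 ill. Minimums: 8 or more infected and 6 or more ill.

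| Infected i | P(I = i) | P(6-7 ill given i) | P(8 or more ill given i) |
|---|---|---|---|
| 8 | 0.1937 | 0.612 | 0.134 |
| 9 | 0.3874 | 0.510 | 0.372 |
| 10 | 0.3487 | 0.340 | 0.610 |

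- Literal ranges both met: 0.1937 × 0.612 + 0.3874 × 0.510 = **0.316**.
- 10 infected, 6-7 ill: 0.3487 × 0.340 = 0.119.
- 8-9 infected, 8 or more ill: 0.1937 × 0.134 + 0.3874 × 0.372 = 0.170.
- 10 infected, 8 or more ill: 0.3487 × 0.610 = 0.213.
- Minimums both met: 0.316 + 0.119 + 0.170 + 0.213 = **0.818**.

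The whole 50-point gap comes from cohorts that did better than one or both ranges. If infection and illness are instead taken as independent, the pair is 0.271 and 0.790.

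**Other illness rates** (infection 90%, illness only in the infected):

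| Illness rate | Literal ranges | Minimums |
|---|---|---|
| 70% | 32% | 82% |
| 60% | 28% | 62% |
| 50% | 17% | 37% |
| 40% | 7% | 16% |

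**Other infection rates.** P(10/10 infected) is 0.9^10 = 0.349, and 0.599 at a true rate of 95%. At 100% the literal infection criterion can never be met.

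**Allowing for the word approximately.** A tolerance of ±5 points changes no count when n = 10. A tolerance of ±10 points (7-10 infected, 5-8 ill) gives 80%, against 95% for the correspondingly relaxed minimums (7 or more, 5 or more), at 70% illness.

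**The case against.** The strongest reply is that nobody would read the criteria this way. They are approximate, they only guide a joint decision, escalation is optional, and all the data are weighed. Section 6.5.1 itself speaks of criteria being achieved, which suggests a threshold, and Sections 3, 4.1 and 4.2 make the intention plain. All of that stands, and it is why the point is minor. It does not remove the defect: Sections 3 and 4.2 send the reader to 6.5.1, and the figures there still carry an upper end.

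The 32% against 82% contrast also depends on a strict reading and a high illness rate. With the ±10-point tolerance it narrows to 78% against 83% at 60% illness, and to 61% against 62% at 50%. Table 4-1 shows diarrhea incidence varying widely, with 0-38% in one Iowa-strain study. Nor is every 10/10 cohort affected: at 50% illness, 17 of the 35 percentage points for 10/10 infected have fewer than 6 ill and miss the illness criterion under either reading. These limits are fair.

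A third argument is that no passage names 80% and 60% as the minimums, and that with 9/10 and 7/10 the pass rate at the planning rates would be 55%. But 8/10 infected with 6/10 ill already satisfies the criteria as written, so using the lower ends changes nothing at the bottom and only removes the cap. The sponsor can confirm this.

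Finally, Section 4.4 on design adaptations is redacted and may hold more detail. The point therefore concerns the visible text.

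**Conclusion.** The point holds and is minor. Section 6.5.1 states a decision threshold that is wrong as written: it caps rates the rest of the protocol wants as high as possible, and it leaves a cohort above the cap to the escalation branch. Under the strict reading at 90% infection and 70% illness, with illness confined to the infected, 50 of every 100 cohorts of 10 would meet both lower figures yet fall outside the literal ranges. That gap shrinks with lower illness rates or a generous reading of approximately. It measures the distance between two readings, not the probability of a wrong dose, which the joint review makes unlikely. No endpoint analysis, confidence interval or sample-size figure changes.

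**What to change.** In Protocol 6.5.1, reword the two bullets as *at least approximately 80% of participants showing infection* and *at least approximately 60% of participants showing diarrheal illness*. Name a single figure in each, because putting *at least* before a range would leave the minimum unclear. Results above these figures then lead to repeating the dose, and the escalation sentence applies only when a minimum is missed.

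At the planning rates, both minimums are met in about 82% of cohorts of 10, under the nested assumption above. The cost is a few words in each of two bullets, with no change to the sample size or the analysis.
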